6.5 Enzyme Estimation of Myocardial Infarct Size

After an acute myocardial infarction, infarct size quantification is clinically important because it correlates with mortality and morbidity (37).

The gold standard for infarct size quantification is cardiac magnetic resonance imaging (CMR). We will use CMR in all subjects in this trial. In addition, biochemical markers remain a realistic and simple method for infarct size estimation. Troponin is a protein complex consisting of three subunits (I, C and T) that modulate the calcium-mediated interaction between actin and myosin in skeletal and cardiac muscle tissue (38).

Circulating levels of highly sensitive troponin not only correlate with infarct size and ejection fraction but also predict clinical outcomes after a ST-segment elevation myocardial infarction (STEMI) (39).

The first articles detailing the relationship between cTnT and infarct size were published in 1993 (40). (41).

All studies have found a consistent and positive correlation between cardiac troponin and infarct size determined by both CMR and SPECT. Therefore, cardiac troponin T (cTnT) can be used as a surrogate measure for this purpose. The 24 hours value of troponin after the onset of symptoms had the nearest associations with all outcomes (42).

In our study, cardiac troponin will be employed as a surrogate endpoint for infarct size.

A blood sample will be taken 24-36 hours post PPCI to determine peak high sensitivity troponin I levels. This blood test is performed routinely in our centre in patients presenting with STEMI and analysis is performed in clinical chemistry department at New Cross Hospital.

6.6 Index of Microvascular Resistance (IMR) Estimation

At the end of the clinical procedure a coronary pressure-/ temperature-sensitive guidewire (Radi Medical Systems, Uppsala, Sweden) will be utilised. The guidewire will be calibrated outside the body then equalized within the guide catheter, with the pressure sensor positioned at the ostium of the guide catheter. The guidewire microsensor will be advanced into the distal third of the culprit artery. The apparent IMR is calculated by multiplying the distal coronary pressure by the mean transit time of a 3 ml bolus of saline at room temperature during coronary hyperaemia induced by intravenous adenosine (43)

Adenosine 140 mcg/kg/min will be used to induce maximal hyperaemia via a large peripheral vein. The mean aortic and distal coronary pressures will be recorded during maximal hyperaemia.

IMR is calculated as the distal coronary pressure multiplied by the mean transit time of the 3-ml saline bolus at maximal hyperaemia, measured simultaneously (automated on the St Jude Medical RadiAnalyzer TM Xpress). This assessment is expected to add no more than thirty seconds to screening time during a coronary angioplasty procedure. Having to screen for duration of thirty seconds long will increase radiation exposure by approximately 3%

6.7 ST Segment Resolution post-acute Myocardial Infarction

Percutaneous coronary intervention is the preferred treatment strategy in patients with acute ST-Elevation myocardial infarction (STEMI). It promotes an early and sustained restoration of epicardial blood flow in the target vessel (17). (45).

Successful reperfusion of the epicardial vessel is essential, but it is the microvascular flow that most strongly correlates with outcome. ST-segment changes reflect myocardial rather than epicardial flow and hence provide prognostic information beyond that provided by coronary angiogram alone (46-49).

The resolution of the ST-segment after the institution of reperfusion therapy is an important

predictor of patency of the artery related to the event and of effective microcirculatory perfusion (50).

Various studies have shown a remarkably consistent relationship between the degree of ST resolution and subsequent mortality (51). ECG is useful, simple, noninvasive, broadly accessible, easily repeatable/applied, and affordable tool (52).

The persistence of ST-segment elevation on the ECG, despite the restoration of a normal epicardial flow, reflects a poor prognosis and correlates with larger infarct size and higher combined rate of severe cardiovascular adverse events (53). In our study, an ECG will be recorded 90-120 minutes post PPCI to assess the degree of ST segment resolution.

6.8 CMR Assessment of Myocardial Infarct Size

CMR has become the gold standard for surrogate endpoints in clinical trials. CMR of myocardial infarction has been correlated with histology (54). It can accurately measure infarct size (55), LV volumes (56), myocardial salvage (57), microvascular obstruction (MVO) (58) and myocardial oedema (area at risk). Myocardial infarct size, myocardial salvage and MVO have all been shown to be associated with worse outcomes.

CMR assessment of final infarct size will be performed at three months post STEMI. Infarct size will be quantified by planimetering the region of hyperintensity in the myocardium 10 minutes following gadolinium contrast administration. We will notify patients and their responsible general practitioners about the CMR examination result in writing.

7. STATISTICS AND DATA ANALYSIS

All statistical analysis will be performed in collaboration with [name], Professor of biomedical statistics at University of Wolverhampton on fully encrypted password-protected computers at New Cross Hospital.

Continuous variables will be compared using parametric and non-parametric tests as appropriate. Dichotomous variables will be compared by Fishers exact test. Logistic regression analysis will be used to predict the significant independent predictors of poor outcome post angiography.

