4. STUDY DESIGN

This is an open label randomised controlled pilot trial. We will enrol 100 patients (50 in each arm). We anticipate the conclusion of subject recruitment in 12 months from the study start date, with a further 6 months for data analysis and manuscript preparation. Patients in the intravenous Cangrelor arm will receive Cangrelor as an initial bolus dose given as per body weight followed by an intravenous infusion for no longer than three hours (The total dose of IV Kengrexal to be administered based on average body weight of 80 Kg is 510 micrograms/kg given over two hours), they will then switch to oral Ticagrelor given at maintenance dose of 90mg twice daily for 12 months. Patients in the oral Ticagrelor arm will receive Ticagrelor at a loading dose of 180mg followed by maintenance dose of 90mg twice daily for 12 months. All the 100 participants will undergo a CMR scan three months post PPCI.

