5.3 RANDOMISATION

Potential patients will be reviewed by a member of the research team before randomisation to confirm eligibility. Once the eligibility of the patient is confirmed by the trial coordinators and the verbal assent is gained, randomisation will be carried out prior to patient's transfer to the cardiac catheter suite. Randomisation will be performed via a secure online web-based service. There will be a single password which will give access for randomisation for the trial on fully encrypted password-protected computers at the heart and lung centre, New Cross Hospital. The system is accessed via a secure connection (SSL) over the internet. This connection encrypts data between the user's internet browser and the server. Online randomisation is achieved by the trial coordinator entering a patient identifier (text field will be unique), own email address and the randomisation system password. Randomisation is by random permuted blocks to oral Ticagrelor or IV Cangrelor in 1:1 ratio. An email notification is generated displaying the chosen treatment group or code and sent to the email address given by the user randomising and the administrator email address. The administrator email address is the one provided when the system is set up (usually a trial coordinator or central trial email address). There is only one password and only members of the research team can perform a randomisation.

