6.4 TIMI Flow Grade

In acute ST elevation myocardial infarction early reperfusion of the occluded coronary artery, limits the size of infarction, reduces the degree of left ventricular dysfunction, and improves survival (32). Assessment of the degree of reperfusion was achieved using the Thrombolysis in Myocardial Infarction (TIMI) flow grading system developed in the TIMI 1 trial (Grade 0—No perfusion; Grade 1—Penetration without perfusion; Grade 2—Partial perfusion; Grade 3—Complete perfusion) (33). A larger improved survival was observed in patients who achieved TIMI grade 3 flow (34, 35). There is a nearly linear correlation between higher rates of early TIMI grade 3 flow and improved survival (35).

In our study, we will assess the index of blood flow through the culprit coronary artery using TIMI Frame Count (TFC). The TFC is a simple, reproducible, objective, and quantitative index of coronary flow that allows standardization of TIMI flow grades and facilitates comparisons of angiographic end points between trials (36).

The number of cine-frames required for contrast to first reach standardized distal coronary landmarks in the infarct-related artery (the TIMI frame count) will be measured with a frame counter on the GE cine-viewer. The first frame to be used for TIMI frame counting will be the first frame in which dye fully enters the artery. The last frame is defined as the frame when dye first enters the distal landmark branch.

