7.1 Sample Size Calculation

A previous open label, multicentre study assessed the pharmacodynamics of Cangrelor in a number of patients with acute coronary syndrome (39 patients) (66). Our study is an open label single centre pilot trial planning to enrol 100 patients. Our study will provide the basis for power calculation for future similar studies. This study is a pilot study and not designed to test or determines clinical outcomes such as mortality, but rather we will be looking at the clinical efficacy of Cangrelor versus Ticagrelor in the context of platelet inhibition and effect on myocardial necrosis. Therefore, no formal sample size calculation has been conducted.

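### Pre-specifying adjustment for two baseline covariates would sharpen the infarct size, troponin and IMR comparisons at little cost; the unadjusted comparison is valid but less precise

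*Combined protocol and SAP*

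**What the plan says.** Section 7 is the whole statistical plan. For continuous outcomes it says "Continuous variables will be compared using parametric and non-parametric tests as appropriate". The only multivariable model is a separate one: "Logistic regression analysis will be used to predict the significant independent predictors of poor outcome post angiography". Its outcome is binary and undefined, and it is not a comparison of the arms on IMR, troponin or infarct size (outcomes b, e and f in section 4.1).

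Section 5.3 says "Randomisation is by random permuted blocks to oral Ticagrelor or IV Cangrelor in 1:1 ratio". The person randomising enters an identifier, an email address and a password, so no patient characteristic can enter as a stratum.

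Eligibility (sections 5.4 and 5.5) restricts neither infarct location nor symptom duration. The 12-hour limit in section 2.1 is background only. The baseline column of Appendix 2 lists medical history and demographic data, but neither infarct location nor onset time by name. The one scheduled ECG is 90-120 minutes after PPCI.

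On prognosis, section 6.4 states that "early reperfusion of the occluded coronary artery, limits the size of infarction".

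**The concern.** In a trial of this size, two sources of variation matter for the myocardial outcomes. Differences between patients that are fixed before randomisation widen the confidence interval if the analysis ignores them. If such a factor also falls unevenly between the arms, its effect is carried into the cangrelor-ticagrelor difference.

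The protocol itself treats time to reperfusion as prognostic. Besides section 6.4, section 5.1 relates outcome to door-to-balloon time. Section 6.5 reports that the troponin value 24 hours after symptom onset tracked outcomes best, yet the trial times its sample from PPCI. Delay before arrival therefore also affects where on the troponin curve the sample falls.

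At stake are the width of the intervals for three outcomes and the usefulness of the variance estimates. Section 7.1 says that the trial will inform the sample size of later studies, and the residual SD after adjustment would be useful for that.

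**Working it through.** **Inputs from the documents.** 50 patients per arm (section 4), unstratified 1:1 permuted blocks (section 5.3), and no covariate in the arm comparison (section 7). There is no design calculation to reproduce: "Therefore, no formal sample size calculation has been conducted". Alpha, power, effect size and SD are not given.

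**Assumptions.** Two-sided 5%; effects in SD units; the two covariates jointly explain R² = 10-30% of outcome variance; anterior share p = 30-50%; all 100 patients analysed, as planned for CMR ("All the 100 participants will undergo a CMR scan three months post PPCI"). Fewer scans would widen both the adjusted and unadjusted intervals and leave their ratio nearly unchanged.

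**Precision.** The unadjusted SE of the arm difference is √(2/50) = 0.20 SD. With two covariates the SE is multiplied by √[(1 − R²)(1 + 2/95)], where 1 + 2/95 is the cost of estimating two coefficients. Equivalent n is 100 divided by the square of that ratio. Power for 0.5 SD uses the noncentral t distribution with noncentrality 0.5/SE, on 98 df unadjusted and 96 df adjusted.

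| R² | SE ratio | SE (SD) | Fall in SE | Equivalent n | Power, 0.5 SD |
|---|---|---|---|---|---|
| Unadjusted | 1 | 0.200 | – | 100 | 70% |
| 2% | 1.000 | 0.200 | 0% | 100 | 70% |
| 10% | 0.959 | 0.192 | 4% | 109 | 73% |
| 20% | 0.904 | 0.181 | 10% | 122 | 78% |
| 30% | 0.845 | 0.169 | 15% | 140 | 83% |

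Break-even is at R² = 1 − 1/(1 + 2/95) = 2.1%.

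**Chance imbalance.** The number of anterior infarcts in each arm is taken as Binomial(50, p), and the difference is computed exactly.

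| p | At least 10 points | At least 16 points | At least 20 points |
|---|---|---|---|
| 30% | 33% | 10% | 4% |
| 40% | 36% | 13% | 5% |
| 50% | 37% | 13% | 6% |

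**Shift in the estimate.** If location alone explains R² of the variance, the anterior versus non-anterior difference is γ = √[R²/(p(1 − p))] SD, and an imbalance d moves the unadjusted estimate by γd. Take p = 45%, so that p(1 − p) = 0.2475. Conditional type I error is the rejection rate given that imbalance.

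| R² (location alone) | γ | d | Shift (SD) | Shift / SE | Conditional type I error |
|---|---|---|---|---|---|
| 10% | 0.64 | 10 points | 0.06 | 0.32 | 5.0% |
| 10% | 0.64 | 20 points | 0.13 | 0.64 | 8.4% |
| 20% | 0.90 | 10 points | 0.09 | 0.45 | 4.9% |
| 20% | 0.90 | 20 points | 0.18 | 0.90 | 11.8% |

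**Overall validity.** In simulations with 4,000 runs per setting and R² from 0.1 to 0.4, overall type I error was 4.8-5.4% for the t-test and 4.4-5.1% for the adjusted model.

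**The case against.** The strongest reply is that the plan is silent on adjustment and does not rule it out. Section 7 never uses the word unadjusted, and a linear model is a parametric method. A reader might infer that the planned analysis cannot remove an imbalance, but the wording is too open to support that. What stands is that no model or covariate is fixed in advance. In an open-label trial, covariates chosen after the data are seen carry less weight than pre-specified ones.

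Second, a reader might take infarct location as an established predictor here. No section links it to any outcome, so it is an assumption. The documents support time to reperfusion, and onset to randomisation is only part of that interval. Nothing in them ties IMR to either variable. This objection stands, and it is why the gain is given as a range that reaches down to nothing.

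Third, a reader might infer that the unadjusted result is biased or its test invalid. It is neither over repeated randomisations, because the 0.20 SD standard error already includes chance imbalance. A 10-point imbalance leaves the conditional error near 5%, and imbalances of 20 points or more are uncommon.

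Fourth, it might seem that having the only CMR at three months ("CMR assessment of final infarct size will be performed at three months post STEMI") loses area at risk as a covariate. Any CMR in this trial would follow allocation, so it would not be a baseline covariate in any case.

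Finally, this is a pilot, its first-listed objective (platelet inhibition) is unaffected, and excluding previous infarction and cardiogenic shock already narrows the population. That lowers the priority but does not remove the benefit.

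**Conclusion.** The point holds as a cheap improvement, not as an error in the plan. Section 7 fixes no adjusted comparison for IMR, troponin or infarct size, and the randomisation does not balance any prognostic factor.

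If the two covariates explain 10-30% of the variance, pre-specified adjustment lowers the SE by about 4-15%, the equivalent of 9-40 more patients. It also removes the linear effect of chance imbalance in those covariates from the estimate. At 10% the gain is small, and near 2% it vanishes. These figures rest on assumed covariate strength, anterior share, effect size and alpha, none of which the documents give.

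**What to change.** In section 7, pre-specify for the three outcomes a linear model with arm, infarct location on the presenting ECG (anterior or not) and log time from symptom onset to randomisation.

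- Analyse IMR and troponin on the log scale. For CMR infarct size, use a robust or bootstrap confidence interval if residuals are skewed.
- Report the adjusted difference with its 95% CI as the main result and the unadjusted parametric or non-parametric test as supportive.
- Keep every patient with an outcome by simple imputation of a missing baseline covariate, for example the overall median taken without regard to arm.
- Do not adjust for door-to-balloon time or anything else after randomisation. Section 6.2.2 starts the two drugs in different places, so allocation could affect that interval.
- Add the two fields to the column of Appendix 2 for the period before PPCI.

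The cost is a paragraph in section 7 and two data fields, with no new procedure and no extra patients. The presenting ECG and the onset time should already be in the clinical record, although Appendix 2 names neither. Some onset times will be imprecise or unknown. If both covariates prove unrelated to outcome, the price is about 1% in the SE (√(1 + 2/95) = 1.01).

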7.1 Sample Size Calculation

A previous open label, multicentre study assessed the pharmacodynamics of Cangrelor in a number of patients with acute coronary syndrome (39 patients) (66). Our study is an open label single centre pilot trial planning to enrol 100 patients. Our study will provide the basis for power calculation for future similar studies. This study is a pilot study and not designed to test or determines clinical outcomes such as mortality, but rather we will be looking at the clinical efficacy of Cangrelor versus Ticagrelor in the context of platelet inhibition and effect on myocardial necrosis. Therefore, no formal sample size calculation has been conducted.

8. END OF STUDY

End of the study will be marked by the last patient's last visit samples when they have been analysed. The data will then be scrutinised, and finally an article summarising the study written and submitted to a peer-reviewed journal for consideration of publication. Positive trial results might lead to implementation of the use of intravenous Cangrelor in clinical practice.

Study termination

The safety monitoring committee/Steering Committee will meet on a regular basis. The trial will be terminated early if there is evidence of unexpected excess bleeding with cangrelor or severe or unexpected complications from the IMR procedure.

9. ADVERSE EVENTS

9.1 **DEFINITIONS**

9.1.1 Adverse Event (AE): any untoward medical occurrence in a patient or clinical study subject. Adverse events will stop being recorded after 36 hours from the index admission.

9.1.2 Serious Adverse Event (SAE): any untoward and unexpected medical occurrence or effect that:

- Results in death
- Is life-threatening refers to an event in which the subject was at risk of death at the time of the event; it does not refer to an event which hypothetically might have caused death if it were more severe
- Requires hospitalisation, or prolongation of existing inpatients' hospitalisation
- Results in persistent or significant disability or incapacity
- Is a congenital anomaly or birth defect

Common expected post-procedural adverse events listed below are the conditions not going to be classed as SAEs:

- Acute renal failure requiring haemodialysis, peritoneal dialysis or haemofiltration
- Ventricular arrhythmia requiring direct-current (DC) cardioversion
- Atrial arrhythmia requiring intervention
- Significant heart block requiring temporary or permanent pacing
- Cardiac tamponade requiring urgent surgical intervention
- Cardiogenic shock requiring intra-aortic balloon pump or other assist device
- Emergency coronary artery bypass graft operation

- Arterial complications
- Blood or platelet transfusion

Medical judgement should be exercised in deciding whether an AE is serious in other situations. Important AEs that are not immediately life-threatening or do not result in death or hospitalisation but may jeopardise the subject or may require intervention to prevent one of the other outcomes listed in the definition above, should also be considered serious.

9.2 **REPORTING PROCEDURES**

All serious adverse events will be reported. Depending on the nature of the event the reporting procedures below will be followed. Any questions concerning serious adverse events reporting will be directed to the Chief Investigator in the first instance.w3433;

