5 PARTICIPANT ENTRY

5.1 CONSENT

Consent will be a two-stage process for patients undergoing PPCI for STEMI. Verbal assent will be brief prior to the PPCI and first blood sample, so as not to lead to a reduction in the quality of patient care (MI outcomes are related to the door to balloon time with PPCI). A

shortened patient information sheet will be read to the patient and if verbal assent is gained it will be recorded in the clinical notes and the site file. This is in line with NRES guidelines that suggest that patients admitted with STEMI are considered as unconscious patients initially.

Following emergency PCI and IMR measurement, when the patient is pain free and has been able to rest, a full patient information sheet will be proffered and written consent sought. If the patient does not want to be part of the trial, he or she will be withdrawn from the study and future tests will not be performed. Treatment will continue in accordance with clinical guidelines. The patients' participation in the trial will last for 3 months. At the end of three months a Cardiac MRI scan will be performed unless there are specific contraindications. Vital status will be determined on discharge and at three months when patients turn up to have their cardiac MRI scan. If a patient fails to attend Cardiac MRI scan appointment in three months' time, a telephone call will be made to the relevant GP to determine the vital status of the patients.

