9.2.1 Non serious AEs

All such events, whether expected or not, will be recorded.

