10.2 Potential Risks and Benefits of Participation

Potential Benefits to Participants: CMR clinical report will be generated and available to clinical care team with assessment of LV function and infarct characteristics that may guide future management.

Potential Harms to Participants: The magnetic fields and radio waves used in cardiac MRI have no side effects. This method of taking pictures of organs and tissues doesn't carry a risk of causing cancer

or birth defects. There is a small risk of side effects due to contrast administration during CMR. Gadolinium contrast medium is generally very safe. Side effects or reactions are uncommon but may occur. The most common adverse reactions are brief headache, nausea (feeling sick) and dizziness for a brief time following the injection. This occurs in 1% to 5% of contrast injections. Infrequently, a feeling of coldness may occur at the injection site. There is a negligible incremental risk of IMR measurement above those for PPCI. IMR measurement is expected to add no more than thirty seconds to screening time during a coronary angioplasty procedure. Having to screen for duration of thirty seconds long will increase radiation exposure by approximately 5% of the total PPCI radiation dose. Blood Sampling from arm: may cause bruising and discomfort.

Benefits to Society: this study will allow better understanding of antiplatelet function in patients with STEMI with potential benefits to future patients.

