Appendix 2: Study Summary Tables

	1	2	3	4	5	6	7	8
Timepoint reference	Prior to PPCI	First IC balloon inflation	End of PPCI (following the life-saving part)	90-120 minutes post PPCI	4 hours post dosing	24-36 hours post dosing (15 ml blood for VASP/VerifyNow and peak Troponin)	Discharge	Three months post PPCI
Eligibility	X							
Medical History	x							
Verbal Assent	x							
Randomisation	x							
Dispensation of treatment	Х							
Initiation of either oral Ticagrelor or IV Cangrelor therapy	X							
Written Informed consent			Х					
Demographic data collection	X							
10ml blood collection for VASP/ VerifyNow		×			X	X		
IMR			Х					
ECG				X				

10ml blood								
collection for						x		
Peak Troponin						^		
Level (routine)								
TIMI Flow			X					
Grade								
Vital Status assessment							X	Х
BARC definition for bleeding			x					
Target Vessel Failure			X					
CMR								Х
Concomitant Medications	X	X	X	X	x	X	X	Х
Adverse Events review	Х	X	X	X	X	X to stop at 36 hours		

Study Steps	Time
1-Quick initial assessment of patients suitable for enrollment in the trial	Upon arrival at the Heart and Lung centre, New Cross Hospital
2-Verbal assent	After the initial assessment
3-Randomisation to either one of the two trial treatment groups	After obtaining verbal assent
4-Initiation of either oral Ticagrelor or IV Cangrelor therapy	Based on randomisation result
5-Primary PCI procedure	Once the second antiplatelet therapy is initiated (Ticagrelor or Cangrelor)
6-Blood sampling for P2Y12 inhibition estimation (using VASP phosphorylation and VerifyNow tests)	A- At the time of first intracoronary balloon inflation (10 ml of blood from the femoral or radial sheath) B- 4 hours post dosing (10 ml of blood from an anticubital vein) C- 24-36 hours post dosing (15 ml in total. 10 ml for VASP/VerifyNow and 5 ml for peak Troponin level. One needle prick)
7-IMR measurement	Immediately following PPCI (same procedure setting)
8-Patient information sheet will be provided and written consent sought	After successful completion of PPCI
9-ECG recording to assess the degree of ST-segment resolution.	90-120 minutes post PPCI

10-Peak Troponin level assessment	24-36 hours post PPCI.
11-TIMI flow grade assessment	Post PPCI
12-Vital Status assessment	On discharge and at three months post PPCI
13-CMR estimation of final myocardial infarct size	At three months post PPCI

STUDY COSTS

CMR	100 scans @ reduced research rate £100	= £10,000

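### Adverse event recording stops at 36 h, so the expected contrast reactions at the three-month research CMR, and some in-hospital events after 36 h, have no planned recording route

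*Combined protocol and SAP*

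**What the plan says.** Section 9.1.1 sets the recording window: "Adverse events will stop being recorded after 36 hours from the index admission". In the Appendix 2 schedule, the last entry in the adverse event review row is in the 24-36 hour column and reads "X to stop at 36 hours". The discharge and three-month columns are empty for that row.

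The CMR is a trial procedure that falls well outside this window. Section 4 says: "All the 100 participants will undergo a CMR scan three months post PPCI". Section 6.8 measures infarct size "following gadolinium contrast administration". Section 5.1 puts the scan inside the trial period: "The patients' participation in the trial will last for 3 months".

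Section 10.2 describes contrast side effects among the potential harms to participants: "The most common adverse reactions are brief headache, nausea (feeling sick) and dizziness for a brief time following the injection". It then gives a rate: "This occurs in 1% to 5% of contrast injections".

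Section 9.2.1, on non-serious events, says: "All such events, whether expected or not, will be recorded". It gives no time limit of its own.

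Section 9.1.2 lists post-procedural conditions that will not be classed as SAEs. They include blood or platelet transfusion, arterial complications and tamponade needing urgent surgery. Section 9.2 requires SAEs to be reported and gives no end date.

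Section 4.2 names BARC bleeding, target vessel failure and vital status at discharge as in-patient safety endpoints. Appendix 2 marks the first two only in the end-of-PPCI column, and vital status at discharge and three months.

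**The concern.** The protocol names a harm of one of its own research procedures and gives its frequency, yet closes adverse event recording about three months before that procedure takes place. A final report listing no non-serious CMR reactions would then reflect the recording rule and would say nothing about whether any occurred.

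The in-hospital gap is narrower but closer to the trial's subject. This is a comparison of antiplatelet regimens, and both arms continue ticagrelor after the procedure. Section 8 makes unexpected excess bleeding with cangrelor a ground for early termination. Some of the conditions barred from SAE status are themselves bleeding events or consequences of bleeding. After 36 h the adverse event route is closed to them, and the schedule has no later bleeding assessment to take its place.

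**Working it through.** The documents give no figure for expected or recorded CMR reactions, so there is none to reproduce. The check has two parts.

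**(a) Reactions at the three-month CMR**

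Inputs:
- Planned scans: n = 100 (section 4; also section 4.1 item f and the cost table).
- Reaction rate per injection: p = 0.01 to 0.05 (section 10.2).
- End of adverse event recording: 36 h after index admission (section 9.1.1, Appendix 2).
- Time of scan: three months after PPCI (sections 4 and 6.8, Appendix 2).

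No scan falls inside the 36 h window, so planned capture of non-serious reactions is 0.

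Expected number of reactions = n × p:
- at 1%: 100 × 0.01 = 1
- at 5%: 100 × 0.05 = 5

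Chance of at least one = 1 − (1 − p)^n, taking patients as independent:
- at 1%: 1 − 0.99^100 = 0.634
- at 5%: 1 − 0.95^100 = 0.994

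Section 5.1 allows for contraindications and missed scan appointments, so 100 is an upper limit. The documents give no dropout rate. Smaller numbers of scans, taken purely as assumptions, give:

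| Scans | Expected at 1% | Expected at 5% | P(≥1) at 1% | P(≥1) at 5% |
|---|---|---|---|---|
| 100 (planned) | 1.0 | 5.0 | 63.4% | 99.4% |
| 90 (assumed) | 0.9 | 4.5 | 59.5% | 99.0% |
| 80 (assumed) | 0.8 | 4.0 | 55.3% | 98.4% |

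In every row, at least one reaction is more likely than not.

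**(b) From 36 h to discharge**

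No arithmetic applies here, because the documents give no event rates. Setting the routes side by side:

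| Type of event after 36 h, before discharge | AE route (9.1.1) | SAE route (9.1.2, 9.2) | Other scheduled item (Appendix 2) |
|---|---|---|---|
| Non-serious event | Closed | Does not qualify | None |
| Condition on the 9.1.2 exclusion list | Closed | Barred by the list | None; BARC and target vessel failure marked only at end of PPCI |
| Serious and unexpected event | Closed | Open, no end date stated | Vital status, if fatal |

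The first two rows have no scheduled route. The list of study steps in Appendix 2 does not supply one: it includes vital status at discharge and three months, but no bleeding or target vessel failure assessment at any time. The overlap with bleeding shows in Appendix 1, where transfusion with overt bleeding is BARC type 3a and cardiac tamponade is type 3b.

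**The case against.** The strongest defence is that the 36 h limit is deliberate. Section 9.1.1 and Appendix 2 state it consistently, and an adverse event summary labelled as covering 36 h is limited, not false. On this view section 9.2.1 does not contradict it, since that sentence concerns whether events were expected and takes its window from 9.1.1. The contrast reactions are brief and mild and bear on none of the objectives in section 3. Both arms have the same scan, so the comparison of cangrelor with ticagrelor is unaffected.

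Most of this stands. The conflict with 9.2.1 is a matter of wording that should be tidied, and the efficacy comparison is not at risk from the CMR gap. It does not answer the main point: a consistently stated window still excludes a harm that the protocol attributes to its own procedure.

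A reader might go further and infer that every in-hospital event after 36 h is lost. The documents do not support that. The limit is attached to adverse events in 9.1.1, while SAE reporting carries no end date. Section 9.1.2 leaves room for medical judgement on seriousness in situations it does not list. Vital status is collected at discharge and at three months, and section 4.1 says in general terms that clinical and safety data will be recorded. That general statement is not a scheduled assessment, however, so it does not fill the gap in (b).

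A reader might also take section 4.2 to run all its endpoints to discharge. Only vital status is tied to discharge there. For bleeding and target vessel failure, the in-patient label and the single end-of-PPCI mark simply need to be reconciled.

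**Conclusion.** The point holds in two limited parts.

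- **CMR visit.** Non-serious contrast reactions at the research scan have no planned recording route. On the protocol's own rate, 100 scans give 1 to 5 expected reactions and a 63% to 99% chance of at least one. This rests on the 1% to 5% rate applying to these patients, on independence between patients and on all planned scans being done. With 80 scans (assumed) the range is 0.8 to 4 reactions and 55% to 98%.
- **36 h to discharge.** Non-serious events and the conditions excluded by 9.1.2 have no scheduled route. The documents allow no estimate of how many events this affects. It matters because excess bleeding is a termination criterion.

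Neither part shows that serious, unexpected events go unreported. The CMR gap does not bias the efficacy comparison. What is affected is the completeness of the safety data. It would be wrong to conclude that the safety summary must be false: if it states its 36 h limit, it is accurate but incomplete. This is a worthwhile low-cost improvement and not a threat to the trial's main results.

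**What to change.** - Amend section 9.1.1 and the adverse event row of Appendix 2 so that adverse events are recorded to discharge.
- Extend the BARC bleeding and target vessel failure rows of Appendix 2 to discharge, in keeping with their in-patient label in section 4.2.
- Add an adverse event check at the three-month CMR visit, limited to reactions to the scan or the contrast.
- Align sections 4.2, 9.1.1 and 9.2.1 with Appendix 2 so that they give one window, and state the SAE reporting window in section 9.2.
- In the report, give the recording window beside every safety table.

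The cost is slightly more data collection at two contacts that already take place. Vital status and concomitant medications are already collected at discharge, and patients attend in person for the CMR. No extra visit or test is needed, and treatment is unchanged.
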